7. STUDY POPULATION ANALYSES

7.1. Planned Analyses Overview

The study population analyses will be based on the “All Subjects” population, unless otherwise specified.

[Table 2](#) provides an overview of the planned study population analyses with full details of data displays being presented in [Appendix 11: List of Data Displays](#).

Table 2 Overview of Planned Study Population Analyses

Display Type	Data Display's Generated		
	Figure	Table	Listing
Randomisation			
Randomisation			Y
Subject Disposition			
Subject Disposition		Y	
Reasons for Screening Failures			Y
Reasons for Withdrawals		Y	Y
Important Protocol Deviations		Y	Y
Deviations Leading to Exclusions from PP Population		Y	Y
Inclusion and Exclusion Criteria Deviations			Y
Demography			
Demographics Characteristics		Y	Y
Race & Racial Combinations		Y	Y
Study Populations		Y	
Medical Condition & Concomitant Medications			
Medical Conditions (Current/Past)		Y	Y
Concomitant Medication		Y	Y

8. PRIMARY STATISTICAL ANALYSES

8.1. Efficacy Analyses

8.1.1. Overview of Planned Efficacy Analyses

The efficacy analyses will be based on the “Analysis Population”, unless otherwise specified.

Table 3 provides an overview of the planned efficacy analyses with full details of data displays being presented in [Appendix 11: List of Data Displays](#).

Table 3 Overview of Planned Efficacy Analyses

ENDPOINT	Absolute						Change from Baseline							
	Stats Analysis			Summary		Individual		Stats Analysis			Summary		Individual	
	T	F	L	T	F	F	L	T	F	L	T	F	F	L
DLco														
Diffusing capacity for carbon monoxide (DLco)	Y			Y	Y		Y	Y			Y	Y		Y

NOTES :

- T = Table, F = Figure, L = Listing, Y = Yes display generated.
- Stats Analysis = Represents TFL related to any formal statistical analyses (i.e. modelling) conducted.
- Summary = Represents TFL related to any summaries (i.e. descriptive statistics) of the observed raw data.
- Individual = Represents FL related to any displays of individual subject observed raw data.

8.1.2. Statistical Model

Analysis of variance (ANOVA) with repeated measure will be performed on DLco. The primary interested outcome is to compare the treatment effects of the two treatments, where the treatment effect is defined as the change of DLco at the end of each treatment period from the corresponding baseline. Methodological differences in how DLco is collected at the two site causes variance differences by site so it will not be possible to pool DLco values across sites.

The model assumes no cross-over effect. This assumption will be tested by the following code:

```
data results;
  set results;
  contrast = 0.5*(baseline_period1 - baseline_period2);
run;

proc ttest alpha=0.10;
  class seq;
  var contrast;
run;
```

Due to the small sample size, this test has a low power to detect cross-over effects, so the assumption will also be tested graphically by looking at a plot of measures overtime. If there are any departures from the distributional assumptions, alternative models will be explored using appropriately transformed data.

9. SECONDARY STATISTICAL ANALYSES

9.1. Efficacy Analyses

9.1.1. Overview of Planned Efficacy Analyses

The secondary efficacy analyses will be based on the “Analysis Population”, unless otherwise specified.

The study is being conducted at two sites. One of these two sites does not have the ability to collect DLno, DM, and Vc. Summaries of DLno, DM, and Vc will only be performed for subjects at the site which this data is collected.

When calculating summary statistics for efficacy data, pooled summaries and summaries for each site individually will be generated. Patient ID's in the PPD are from the Mayo Clinic and patients ID's in the PPD are from Hennepin.

[Table 4](#) provides an overview of the planned efficacy analyses with further details of data displays being presented in [Appendix 11: List of Data Displays](#).

All change from baseline table, listing, and figures, use the baseline measured just prior to the period, (i.e. period 1 measurements use the baseline measured just prior to period 1 and period 2 measures use the baseline measured just prior to period 2), unless otherwise specified.

Statistical analysis (adjusted means and/or posterior means) will be performed on secondary endpoints as shown in Table 4

Table 4 Overview of Planned Efficacy Analyses

Endpoint	Absolute						Change from Baseline					
	Stats Analysis		Summary		Individual		Stats Analysis		Summary		Individual	
	T	F	T	F	F	L	T	F	T	F	F	L
Diffusing capacity for nitric oxide (DLno)	Y		Y	Y	Y	Y			Y	Y	Y	Y
Membrane conductance (DM)	Y		Y	Y	Y	Y			Y	Y	Y	Y
Capillary blood volume (Vc)	Y		Y	Y	Y	Y			Y	Y	Y	Y
Dm/Vc	Y		Y		Y				Y			
Diffusing capacity for carbon monoxide (DLco) following exercise			Y	Y	Y	Y			Y	Y	Y	Y
Diffusing capacity for carbon monoxide (DLco) following saline infusion			Y	Y	Y	Y			Y	Y	Y*	Y
VE/VCO ₂ ratio			Y	Y	Y	Y			Y	Y	Y	Y
Forced vital capacity (FVC)			Y	Y	Y	Y			Y	Y		Y
Forced expiratory volume in 1 second (FEV1)			Y	Y	Y	Y			Y	Y		Y
Forced expiratory flow, FEF25-75			Y	Y	Y	Y			Y	Y		Y
Forced expiratory flow, FEF50			Y	Y	Y	Y			Y	Y		Y
Forced expiratory flow, FEF75			Y	Y	Y	Y			Y	Y		Y
Respiratory rate (Preventice Body Guardian)			Y	Y	Y							
Troponin			Y			Y			Y			Y
SF-36 acute score			Y			Y			Y	Y		
Dyspnea score			Y			Y			Y	Y		Y

*Change from value is calculated by taking the post-saline measure to the prior saline measure

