7.3.2. Submaximal Exercise Test

Blockade of the TRPV4 channel with GSK2798745 may decrease pulmonary edema resulting in an increase in exercise capacity and/or oxygen uptake.

Subjects will be asked to participate in a submaximal exercise test that consists of 3 parts: a 2-minute resting baseline, a 3-minute step exercise, and a 1-minute recovery period [Woods, 2011]. Throughout the test, breathing pattern, gas exchange, and heart rate will be monitored using a simplified gas analysis system (i.e. SHAPE Medical Systems, Inc). Respiratory exchange ratio (RER) and the Borg Rating of Perceived Exertion (RPE) measures will be utilized to ensure subjects perform progressive exercise while maintaining a submaximal level throughout the exercise period. Minute ventilation, breath frequency, tidal volume, oxygen consumption, carbon dioxide production, RER and end tidal CO₂ will be obtained from the breath-by-breath gas measurements. The ventilation/carbon dioxide production (VE/VCO₂) slope and other variables will be derived from this data.

The exercise protocol will be completed on Day -1 and Day 7 of each study period. DLco/DLno measurements will be obtained before and after the exercise challenge. Additional details of the exercise protocol for the 3-minute step test are provided in the SRM.

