9.4.2. Secondary Analyses

For other diffusing capacity pharmacodynamic (PD) endpoints such as DLno, D_M and V_c , similar analyses as in Section 9.4.1 will be provided, as data permit. For these PD endpoints, which may be \log_e transformed prior to analysis to satisfy model assumptions, point estimates and their associated 95% confidence intervals will be back-transformed to provide point estimates and 95% confidence intervals for the ratios.

For pulmonary function measurement endpoints such as FVC, FEV1, FEF_{25-75} FEF_{50} , and FEF_{75} , FRC and EELV, similar analysis as in Section 9.4.1 will be provided, as data permit. For these PD endpoints, which may be \log_e transformed prior to analysis to satisfy model assumptions, point estimates and their associated 95% confidence intervals will be back-transformed to provide point estimates and 95% confidence intervals for the ratios.

For respiratory rate measurement and dyspnea score, similar analysis as in Section 9.4.1 will be provided, as data permit.

In terms of DLco and DLno changes from baseline after saline challenge on Day 5 and after exercise on Day 7, the change from baseline for the challenge (after-before) will be calculated and summarized in tabular format by treatment. A statistical analysis will be performed using a mixed effect model with a fixed effect term for treatment, period and sequence, random effect term for subject-within-sequence, and baseline as a covariate, if data permit. Point estimates and associated 95% confidence intervals will be constructed for the differences between the active treatment and placebo.

In terms of ventilatory efficiency, scatter plots for Ve/VCO₂ at Baseline and Day 7 will be performed and the slope or correlation of Ve/VO₂ provided. Summary statistics for Ve and VCO₂ and change from baseline measurement will be provided.

Details on the analysis of other endpoints will be provided in RAP.

Pharmacokinetic analyses will be the responsibility of the Clinical Pharmacology Modeling & Simulation Department within GlaxoSmithKline. Plasma GSK2798745 concentration-time data will be analyzed by non-compartmental methods with the latest available version of WinNonlin software. Calculations will be based on the actual sampling times recorded during the study. From the plasma concentration-time data, the pharmacokinetic parameters such as Cmax and AUC may be determined, as data permit.

The details of the PK analysis will be listed in the RAP.

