3.2. Study Objective(s) and Endpoint(s)

Objectives	Endpoints
Primary Objectives	Primary Endpoints

 To assess the effect of GSK2798745 on pulmonary gas transfer 	
 Change in the diffusing capacity for carbon monoxide (DLco)
Secondary Objectives	Secondary Endpoints

 To assess the effect of GSK2798745 on alveolar-capillary conductance (DM) 	
 Change in the diffusing capacity for nitric oxide (DLno), membrane conductance (DM), and capillary blood volume (Vc)

 To assess the effect of GSK2798745 on pulmonary gas transfer following exercise and following an intravenous saline infusion 	
 Change in diffusing capacity for carbon monoxide (DLco)

 To evaluate the effect of GSK2798745 on ventilatory efficiency 	
 Change in the VE/VCO₂ slope determined during a standardized 3-minute step test

 To evaluate the effect of GSK2798745 on pulmonary function 	
 Changes in spirometry measures including forced vital capacity (FVC) and forced expiratory volume in 1 second (FEV1) as well as forced expiratory flows, FEF25-75 FEF50, and FEF75 Change in functional residual capacity (FRC) and end-expiratory lung volume (EELV) measured by body plethysmograph

 To assess the effect of GSK2798745 on dyspnea 	
 Change in dyspnea score

 To assess the effect of GSK2798745 on respiratory rate 	
 Change in respiratory rate continuously measured by body sensor (Preventice Body Guardian)

 To evaluate the safety and tolerability of repeat administration of GSK2798745 	
 Clinical monitoring of vital signs, ECGs, and clinical laboratory safety data, including LFTs and troponin as well as reporting of adverse events (AEs)

 To assess the effect of GSK2798745 on quality of life 	
 Change in SF-36 acute score

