11.13.5. Efficacy Tables

Efficacy Tables					
No.	Population	IDSL / TST ID / Example Shell	Title	Programming Notes	Deliverable [Priority]
DLco					
2.01	Analysis	Non-Standard EFF_T1	Summary Statistics of DLco	DLco has measures on Baseline, Day 4, 5, and 7 for each treatment period and follow-up. Create this table twice, one table with only Mayo patients and another table with only Hennepin patients	IA, SAC [2]
2.02	Analysis	Non-Standard EFF_T2	Summary Statistics of DLco Change from Baseline	Create this table twice, one table with only Mayo patients and another table with only Hennepin patients	IA, SAC [2]
2.03	Analysis	Non-Standard EFF_T12	Summary Statistics of DLco Change from Intervention	Create this table twice, one table with only Mayo patients and another table with only Hennepin patients. This should be the Mean and SD of the Post-Pre difference.	IA, SAC [2]
2.04	Analysis	Non-Standard EFF_T6	Summary of Statistical Analysis Results of DLco	Models should be run with only Mayo patients. Hennepin patients are excluded because of methodological differences.	IA, SAC [2]
Alveolar-capillary Conductance (D_M)					
2.05	Analysis	Non-Standard EFF_T3	Summary Statistics of Gas Transfer Tests	DLno, Dm, Vc, and Dm/Vc have measures on Baseline, Day 4, 5, and 7 for each treatment period and follow-up	SAC [2]
2.06	Analysis	Non-Standard EFF_T2	Summary Statistics of Gas Transfer Tests Change from Baseline	DLno, Dm, Vc, and Dm/Vc have measures on Baseline, Day 4, 5, and 7 for each treatment period and follow-up. Baseline is day -1 for exercise and chronic values, but should be calculated as post minus pre for Saline.	SAC [2]

Efficacy Tables					
No.	Population	IDSL / TST ID / Example Shell	Title	Programming Notes	Deliverable [Priority]
2.07	Analysis	Non-Standard EFF_T12	Summary Statistics of Gas Transfer Tests Change from Intervention	DLno, Dm, Vc, and Dm/Vc have measures on Baseline and Day 5 and 7 for each treatment period. This should be the Mean and SD of the Post-Pre difference.	IA, SAC [2]
Ventilatory Efficiency					
2.08	Analysis	Non-Standard EFF_T7	Summary Statistics of VE/VCO ₂ Ratio	VE/VCO ₂ ratio has measures on Baseline and Day 7 before and after 3-minutes step test. Create this table twice, one table with all patients and another table with Hennepin patients excluded from the statistics.	SAC [2]

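### The SAP silently drops the protocol's treatment-difference model for the saline and exercise DLco/DLno challenges, derives no VE/VCO2 slope and gives FRC/EELV no output

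*SAP*

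**What the plan says.** **Challenges.** For the after-minus-before change in DLco and DLno (saline on Day 5, exercise on Day 7), Protocol 9.4.2 states: "A statistical analysis will be performed using a mixed effect model with a fixed effect term for treatment, period and sequence". It adds a random subject-within-sequence term and a baseline covariate, and asks for active minus placebo with 95% CIs, if data permit. SAP 9.1.1 limits secondary modelling: "Statistical analysis (adjusted means and/or posterior means) will be performed on secondary endpoints as shown in Table 4". In Table 4 the Stats Analysis cells are blank for DLco after exercise and after saline, and DLno has no challenge row. For the tables that do cover these changes, 2.03 (DLco) and 2.07 (DLno, DM, Vc, Dm/Vc), the programming note is "This should be the Mean and SD of the Post-Pre difference".

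**Ventilatory efficiency.** Protocol 7.3.2 says the VE/VCO2 "slope and other variables will be derived from this data". SAP 3.2 keeps the endpoint as "Change in the VE/VCO₂ slope determined during a standardized 3-minute step test". The SAP's output is Table 2.08, "Summary Statistics of VE/VCO ₂ Ratio", with its change-from-baseline companion, Table 2.09.

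**Other secondary endpoints.** Protocol 9.4.2 plans primary-type models for spirometry and lung volumes ("FRC and EELV, similar analysis as in Section 9.4.1 will be provided, as data permit") and further: "For respiratory rate measurement and dyspnea score, similar analysis as in Section 9.4.1 will be provided, as data permit".

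**Declared changes.** SAP 3.1 reports no change or deviation from the analysis in protocol amendment 02. SAP Section 2 records only the removal of the exploratory Bayesian analysis and the addition of some displays.

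**The concern.** Gas transfer after exercise and after saline is a named secondary objective, and Protocol 4.4 chose the crossover so that each subject acts as his or her own control. Means and SDs by arm do not deliver that comparison. With complete pairs, the difference between arm means still estimates the treatment difference. Its paired confidence interval and the period adjustment are lost. The standard error of the difference cannot be obtained from two arm SDs without the within-subject correlation.

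For ventilatory efficiency, the protocol planned no treatment-difference model, so what is lost is the endpoint itself: the slope is named but never computed. FRC and EELV are named and never shown. Because SAP 3.1 says nothing changed, a reader of the report would have no warning of any of this.

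**Working it through.** **1. Protocol 9.4.2 against SAP Table 4 and Appendix 11**

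| Model-based analyses in Protocol 9.4.2 (if or as data permit) | Number | Marked in Table 4 | Results table in Appendix 11 |
|---|---|---|---|
| DLno, DM, Vc | 3 | 3 | 0 |
| FVC, FEV1, FEF25-75, FEF50, FEF75, FRC, EELV | 7 | 0 | 0 |
| Respiratory rate, dyspnea | 2 | 0 | 0 |
| DLco and DLno, after saline and after exercise | 4 | 0 | 0 |
| Total | 16 | 3 | 0 |

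Table 2.04 is the only statistical results table in Appendix 11. It covers primary DLco at the Mayo site, and SAP 8.1.2 defines its effect as the end-of-period change from baseline, which is not the challenge response. Table 4 was read from a PDF, but its blank cells agree with the Appendix 11 list, so they are not an extraction fault.

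**2. Tracing the slope and the lung volumes**

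Table 4, Tables 2.08 and 2.09, Figures 2.45 to 2.50 and Listings 30 and 31 all use the VE/VCO2 ratio or its values at each time point. No regression, slope or correlation is defined, and SAP Appendix 5 contains no efficacy derivations. FRC and EELV are in SAP 3.2 but in no Table 4 row, table, figure, listing or shell. The pulmonary function displays name only FVC, FEV1 and the three flows.

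**3. What the paired interval is worth**

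Method check against the protocol's own figure: the crossover half-width is t(0.975, n−2) × SDw × √(2/n). With n = 12 and SDw = 1.5 this gives 1.364, matching the 1.36 in Protocol 9.2.

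With equal arm SDs and within-subject correlation ρ, the ratio of unpaired to paired SE is 1/√(1−ρ). Allowing for degrees of freedom, the ratio of the interval a reader would build from the arm SDs to the crossover interval is

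[t(0.975, 2n−2) / t(0.975, n−2)] / √(1−ρ).

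| | ρ = 0 | 0.25 | 0.5 | 0.75 |
|---|---|---|---|---|
| SE ratio | 1.0 | 1.15 | 1.41 | 2.0 |
| Half-width ratio, n = 11 | 0.92 | 1.06 | 1.30 | 1.84 |
| Half-width ratio, n = 6 | 0.80 | 0.93 | 1.13 | 1.61 |

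The 11 comes from SAP 4.1: 10 subjects in the Bayesian prediction plus one more. The 6 is an assumed number for a single site. Every ρ is an assumption.

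**4. Period effect left in the raw difference**

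Without period adjustment, the difference in arm means carries the fraction (nPA − nAP)/n of any period effect. For assumed sequence splits this is 1/11 = 0.09 at 5:6, 3/11 = 0.27 at 4:7 and 2/6 = 0.33 at 2:4.

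**The case against.** **The protocol models are conditional.** The SAP records facts that bear on the condition: DLco cannot be pooled across sites, one site cannot collect DLno, DM or Vc, and enrolment stopped early. Saline pairs may be fewer still, because Protocol Appendix 9 withholds the infusion in some subjects and can remove the challenge altogether. All this could justify simpler analyses. But the SAP never invokes the condition, and it states that nothing changed.

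**SAP 9.1.1 is open about limiting models to Table 4.** True, but that makes the SAP inconsistent with its own Section 3.1 and does not declare the departure.

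**The DLno row is marked, and its shell includes post-challenge visits.** The mark is under absolute values, and no results table follows from it. Read generously, the marked count becomes 3 + 2 = 5 of 16. The results-table count stays at 0.

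**Other displays carry relevant information.** Figures 2.09 to 2.11 and 2.20 to 2.22 give 95% CIs by treatment for exercise and saline changes. Figures 2.12 and 2.23 and Listings 28 and 29 show individual values, so a reader could rebuild the paired saline contrast. That is a fair limit on the harm, but the by-treatment intervals are not a treatment contrast, and the listing shells show no Day 7 rows for exercise. Figure 2.42 plots DLco challenge changes and may show a contrast. Its image is not available, its note says the printed values are mean change from baseline, and it names no model. Figure 2.66 has the same gap. Figure 2.49 prints an active-placebo difference for the VE/VCO2 ratio, with no CI specified.

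**The sizes rest on assumptions.** They do. The baseline covariate would also cost a degree of freedom. Using n−3 with the residual variance unchanged, the n = 6 ratios become 0.70, 0.81, 0.99 and 1.40. The value at ρ = 0.5 then falls just below 1, but the conclusion that the error can go either way is unaffected.

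**Protocol 9.4.2 accepts slope or correlation, and writes Ve/VO2 at that point.** The SAP supplies neither, and its own endpoint list says slope.

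**Conclusion.** The concern holds. The SAP omits the protocol's challenge model, derives no VE/VCO2 slope, gives FRC and EELV no output, and reduces spirometry, respiratory rate and dyspnea to summaries. Its statement of no deviation is therefore wrong as written. The size that rests on the documents alone is the count: 16 planned, 3 marked, 0 with a results table. The half-width ratios and period fractions depend on assumed correlations, a one-site sample size and sequence splits. They show the direction and scale of what could go wrong, and the conclusion does not rely on them. This is an estimation study in phase 2a and the heart failure work on the asset has been discontinued, so the point should be fixed but does not threaten the primary analysis.

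**What to change.** In SAP 9.1 and Appendix 11:

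- **Challenges.** Add the Protocol 9.4.2 mixed model for the Day 5 and Day 7 post-minus-pre change, stating whether the baseline covariate is the same-day pre-challenge value. Add a results table of active minus placebo with 95% CI. Run DLco on Mayo patients only, as in Table 2.04, or by site; run DLno only where it is collected. If the data do not support the model, give the mean within-subject difference with a paired 95% CI and the number of complete pairs.
- **VE/VCO2.** Derive the slope per subject and test from the breath-by-breath data and report its Day 7 minus Day −1 change by treatment, with the ratio as supportive. A crossover-model difference is optional.
- **FRC/EELV.** Report with the primary-type analysis as data permit, or say why not.
- **DLno, DM, Vc, spirometry, respiratory rate, dyspnea.** Add the planned results tables or state that the models are dropped. An ordinal summary of the 5-point dyspnea score is defensible if declared.
- **Figures 2.42 and 2.66.** State the model and contrast behind them.
- **SAP 3.1.** List every remaining departure and its reason.

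The cost is low: SAP text and programming on measurements the protocol already schedules, with no new procedures. Whether the breath-by-breath and plethysmography data reached the database from both sites should be confirmed first, since the documents do not show it. The models may be imprecise with so few subjects, hence the paired fallback.
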